**Secondary outcomes:**

**SA1:** We will evaluate symptom-triggered interventions (nursing follow-up calls, unplanned clinic visits and phone referral to clinic, pain management referrals, and adverse event detection) and rates of adverse events up to 30 days after ambulatory cancer surgery. We will also evaluate the number of readmissions up to 30 days. Adverse events will be defined according to the nomenclature established in the MSKCC Surgical Secondary Events Grading System.

**SA2:** We will evaluate patient engagement, patient anxiety, and caregiver burden with the experience of care using validated PROs measures and qualitative interviews.

- Patient engagement will be evaluated preoperatively and at 2 weeks and 2 months postoperatively using the Patient Activation Measure (description below).
- Patient anxiety will be measured on a daily basis for 10 days following surgery using three PRO-CTCAE Anxiety questions.
- Caregiver burden will be evaluated at 2 weeks and 2 months postoperatively among consenting caregivers using the Caregiver Reaction Assessment (description below). Each participating patient will be asked to identify a caregiver, who will then be invited to participate.
- Patient engagement and caregiver burden will also be evaluated using qualitative interviews, with a sample of each of the randomized cohorts, as described below.

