For the endpoints of patient engagement (SA2a) and caregiver burden (SA2c), we will use linear regression with randomization strata as covariates for each subscale separately. For all analyses, we will report an estimate of the difference between groups along with a 95% CI and a two-sided P value for the null hypothesis of no difference between groups. For the endpoint of patient anxiety (SA2b), as measured by the PRO-CTCAE, we will enter daily anxiety scores as a continuous outcome variable into a longitudinal mixed effects model with time, treatment, and treatment by time interaction as predictors and randomization strata as covariates. As all data are collected after randomization, both the treatment term and the treatment by time interaction term are valid indicators of a treatment effect. We hypothesize that initial anxiety will be similar between groups and will be related to immediate postoperative concerns. Subsequent anxiety may be related to emergent symptoms, whether they are considered worrying and how they are dealt with. Hence, we will treat the time by treatment interaction as the primary hypothesis for the purpose of establishing the treatment effect of enhanced feedback on patient anxiety.

In exploratory analysis, the mean of each PRO-CTCAE item (0–4 scale) will be compared between groups during the 10-day post-surgery daily reporting period using the same longitudinal mixed effects model described above for anxiety with time, treatment, and treatment by time interaction as predictors and randomization strata as covariates. All available data will be used in these models. This likelihood-based approach to the analysis of longitudinal PRO data provides valid estimates of intervention effects in the presence of ignorable missing data and is known to be robust to nonignorable missing data if covariates and previous values of the outcome explain much of the missingness.

Supplemental analysis will also employ longitudinal mixed ordinal logistic models to compare ordinal PRO-CTCAE scores between arms.

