### **Data sources and data linkage plans**

Many of the study endpoints will be obtained from MSKCC's institutional database. Endpoints such as MSKCC emergency department visits, nursing follow-up calls, clinic visits, and intrainstitutional referrals are automatically captured as part of electronic medical record (EMR)-enabled care management. Emergency department visits at outside institutions will be captured by a question on our daily symptom surveys and routine follow-up surveys. Responses to the follow up surveys will be captured electronically via MSK Engage. Patients describing an emergency department visit at an institution other than MSKCC are contacted by clinical staff for further details as a routine part of follow-up care. Adverse events are captured by the MSKCC Secondary Surgical Event database. Outside emergency department visits and admissions for patients participating in MSKCC's electronic health information exchange will also be utilized. Electronic health information exchange is carried out through organizations known as Health Information Exchanges (HIEs) or Regional Health Information Organizations (RHIOs). This data is captured within MSKCC's institutional database. Data for all patients who choose to opt out of the health information exchange program will not be used. To note: MSK may join additional HIEs or RHIOs in the future. Any available HIE or RHIO data for participating patients will be collected. PROs are obtained through MSKCC's symptom monitoring software, the same software used to implement symptom self-reporting. Covariates such as age, sex, and race are routinely captured in the MSKCC EMR. Comorbidities are captured by an MSKCC platform used to take the baseline medical history in all surgical patients potentially eligible for ambulatory cancer surgery. Caregivers' responses to the Caregiver Reaction Assessment questionnaires will be

collected via REDCap, a secure web application for building and managing online surveys and databases. In the event the REDCap survey is unavailable, a hardcopy form will be provided to caregivers to complete.

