### **12.3 Randomization**

At the time of protocol consent, it will be explained to patients that they will be completing symptom self-reported questionnaires for up to 30 days after surgery (daily for postoperative days 1 to 10 and then at tailored time points) as a component of routine care, and they will be asked whether they are willing to be randomized to potentially receive additional information that may help them interpret the severity of their symptoms. Randomization will be implemented through CRDB, a fully secure, password-protected database that ensures full allocation concealment. It will be performed within 1 week of the patients' surgical visit. Randomization will be stratified by procedure and will be implemented by randomly permuted blocks of random length. The trial will not be blinded, as it relies on patient knowledge (i.e., how a patient's scores compare with other patients' scores) as a key part of the intervention.

Stratification will be based the following surgical procedure types:

- Gynecologic
  - Laparoscopic or robotic procedure
  - Laparotomy
  - Other
- Breast/Plastics
  - Mastectomy alone (with or without sentinel node and axillary node dissection)
  - Lumpectomy (with or without sentinel node and axillary node dissection)
  - Tissue expander placement
  - Other
- Urology
  - Prostatectomy laparoscopic or robotic
  - Partial or total nephrectomy- laparoscopic or robotic
  - Laparotomy
  - Other
- Head and Neck
  - Thyroidectomy
  - Other

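### The SA2b anxiety model adjusts only for procedure stratum, so protection against missing diaries rests almost wholly on earlier scores and the treatment main effect is less precise than it could be

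*Combined protocol and SAP*

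**What the plan says.** Section 4.2 (secondary outcomes) sets the measurement: "Patient anxiety will be measured on a daily basis for 10 days following surgery using three PRO-CTCAE Anxiety questions". The schedule in Section 7.0 agrees; the only questionnaire before surgery is the Patient Activation Measure (PAM), whose window runs from consent to POD1.

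Section 11.0 fits daily anxiety in a longitudinal mixed model with "time, treatment, and treatment by time interaction as predictors and randomization strata as covariates". It acknowledges that there is no baseline score ("As all data are collected after randomization") and names the test that counts: "we will treat the time by treatment interaction as the primary hypothesis". The exploratory symptom models use the same structure.

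On incomplete diaries, Section 11.0 uses all available data and says that the likelihood approach "is known to be robust to nonignorable missing data if covariates and previous values of the outcome explain much of the missingness".

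On covariates, Section 12.3 says: "Randomization will be stratified by procedure and will be implemented by randomly permuted blocks of random length". The data sources paragraph adds: "Covariates such as age, sex, and race are routinely captured in the MSKCC EMR". It also lists comorbidities as captured, and the heterogeneity paragraph says education is obtained routinely at baseline.

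**The concern.** The plan's robustness statement has two legs: covariates and earlier outcome values. For SA2b the covariate leg is procedure stratum alone. The other leg does not exist for a patient who files no diary: that patient contributes nothing to the likelihood, and no covariate related to anxiety is there to make the absence ignorable. The trial is unblinded and one arm sees its scores against norms, so reporting behaviour could differ by arm. The missing-data section concedes that nonresponse on activation may be nonignorable. Its shifted-percentile imputations, however, are specified for activation and the caregiver measure, and no such analysis is written for the anxiety diary.

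Precision is the second issue. The background section expects heightened anxiety in these patients around surgery. Stable differences between patients that a preoperative score could partly explain stay in the variance of the treatment main effect.

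**Working it through.** **Inputs from the documents.** 2,750 patients allocated 1:1, so 1,375 per arm; 10 daily scores on a 0-12 scale; 3 + 4 + 4 + 2 = 13 procedure strata. The documents give no SD, correlation, power or diary completion rate for SA2b, so there is no plan figure to reproduce. The values below are assumptions. Time is taken as linear; the plan does not state its form.

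**1. Precision of the 10-day mean difference.** Set the variance of one daily score to 1, with intraclass correlation ICC, and let r be the correlation of a preoperative score with the patient's stable level.

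- Variance of a 10-day mean = ICC + (1 - ICC)/10.
- After baseline adjustment, subtract r² × ICC.
- SE ratio = square root of (after/before). Equivalent gain in patients = before/after - 1.

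| ICC | r | Before | After | SE ratio | Gain in n |
|---|---|---|---|---|---|
| 0.5 | 0.3 | 0.550 | 0.505 | 0.958 | 9% |
| 0.5 | 0.6 | 0.550 | 0.370 | 0.820 | 49% |
| 0.7 | 0.3 | 0.730 | 0.667 | 0.956 | 9% |
| 0.7 | 0.6 | 0.730 | 0.478 | 0.809 | 53% |

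The SE therefore falls by about 4-19%. A generalized-least-squares check (intercept SD 2.0, residual SD 1.5, no link between baseline and slope) gives ratios of 0.96, 0.87 and 0.73 at r = 0.3, 0.5 and 0.7. The gain shrinks if baseline is negatively related to the slope: with slope SD 0.14 per day and a baseline-slope correlation of -0.5, the ratio is 0.99 at r = 0.3.

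**2. Precision of the treatment-by-time interaction.** The slope is a within-patient contrast, so a patient's stable level cancels. In the same check, a baseline main effect leaves the interaction SE ratio at 1.00. Adding baseline × time, with baseline-slope correlations of -0.3 and -0.5, gives 0.98 and 0.95. The gain is 0-5%.

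**3. Never-reporters.** Simulation with 2,750 patients, no true effect, and the odds of never reporting doubling per SD of baseline anxiety in Enhanced Feedback only (27% never report there, 25% in Team Monitoring).

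- Mean contrast without baseline: bias -0.069 in units of the SD of one daily score, SE 0.036. The ratio is 0.069/0.036 = 1.9 SE, in favour of Enhanced Feedback. The false-positive rate is about Φ(-1.96 + 1.9) = Φ(-0.06) = 48%. With baseline, the bias is -0.001.
- Interaction, baseline unrelated to slope (ICC 0.6, r 0.5): mean z 0.05, false positives 5.5%, which is nominal.
- Interaction, baseline correlated -0.4 with slope (and 0.6 with level): bias of about 1.0-1.1 SE. At 1.0 SE the false-positive rate is Φ(-0.96) + Φ(-2.96) = 0.169 + 0.002 = 17%. Baseline plus baseline × time brings it back close to 5%.

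**4. Diaries that stop.** Simulation with intercept SD 2.0, slope SD 0.14, residual SD 1.5 and 31-37% of entries missing. Figures are the bias in the interaction, in points per day; its SE is about 0.010-0.012.

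| Missingness depends on | No baseline | Baseline + baseline × time |
|---|---|---|
| Previous score, opposite direction by arm | -0.0001 | -0.0001 |
| Preoperative anxiety, same direction in both arms | 0.0014 | 0.0014 |
| Preoperative anxiety, opposite direction by arm | 0.0105 (about 0.9 SE; day-1 bias -0.21 points) | -0.0001 |
| Current unseen score, opposite direction by arm | -0.042 | -0.048 |

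A baseline score helps in the third row, is not needed in the first two, and does not help the interaction in the fourth.

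**The case against.** The strongest reply is that the plan tests the interaction as primary, and there the precision gain is close to nil. Randomization keeps the comparison valid without a baseline score, and the endpoint is secondary. All of this stands, and it limits the point to a modest one.

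A reader might go further than the documents allow in four ways.

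- *That the model has no patient-level covariate.* Procedure stratum is one, with 13 categories, and the heterogeneity models bring in age and education.
- *That protection against missing diaries is removed.* Earlier scores remain in the likelihood, so it is weakened, chiefly for patients with no entry or very early loss.
- *That the primary SA2b test carries a 48% false-positive rate.* That figure belongs to the mean contrast under one assumed mechanism. In that setting the interaction is nominal unless baseline anxiety also predicts the slope.
- *That patients who quit after seeing themselves above the norm would bias the result.* Feedback displays what the patient has already reported, so such a patient has an earlier score in the model. Simulating that story (Enhanced Feedback patients stopping according to their last reported score, 20% of entries missing, no baseline) gave false-positive rates of 5.3% for the main effect and 6.0% for the interaction, with no material bias.

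It is also fair to say that the missing-data section plans to compare missingness patterns by arm and baseline characteristics of those with and without data. If applied to the diary, that would reveal a problem but would not adjust the SA2b estimate for it.

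**Conclusion.** The point holds as an efficiency and missing-data weakness, not as an invalid analysis. Robustness to missing anxiety diaries rests almost wholly on earlier scores, which never-reporters lack, while useful baseline covariates go unused. Under the assumed ICC of 0.5-0.7 and baseline correlation of 0.3-0.6, the SE of the 10-day mean difference could fall by about 4-19%, or less if anxious patients also improve faster. For the declared primary interaction the gain is about 0-5%.

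The bias scenario needs never-reporting that is driven by preoperative anxiety and differs by arm. The documents neither support nor exclude that, since they give no diary completion rate. Where it occurs, it affects mainly the mean contrast. The case for change is that the remedy costs little and that Section 11.0 also calls the treatment term a valid indicator of effect.

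**What to change.** (a) Add the three PRO-CTCAE anxiety items to the existing preoperative PAM contact, and require completion before randomization, because the present PAM window extends to POD1. Enter baseline anxiety and baseline × time in the SA2b model.

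(b) Prespecify age, sex, education and comorbidity as covariates in the SA2b model and the exploratory symptom models. Use the preoperative PAM score only where it was completed before randomization.

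Cost: three extra items per patient, a rule for missing baseline scores, and SAP wording. Part (b) needs no new data collection. Neither part deals with missingness that depends on the current unseen score, so the revised text should not claim that it does.

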### **Data sources and data linkage plans**

Many of the study endpoints will be obtained from MSKCC's institutional database. Endpoints such as MSKCC emergency department visits, nursing follow-up calls, clinic visits, and intrainstitutional referrals are automatically captured as part of electronic medical record (EMR)-enabled care management. Emergency department visits at outside institutions will be captured by a question on our daily symptom surveys and routine follow-up surveys. Responses to the follow up surveys will be captured electronically via MSK Engage. Patients describing an emergency department visit at an institution other than MSKCC are contacted by clinical staff for further details as a routine part of follow-up care. Adverse events are captured by the MSKCC Secondary Surgical Event database. Outside emergency department visits and admissions for patients participating in MSKCC's electronic health information exchange will also be utilized. Electronic health information exchange is carried out through organizations known as Health Information Exchanges (HIEs) or Regional Health Information Organizations (RHIOs). This data is captured within MSKCC's institutional database. Data for all patients who choose to opt out of the health information exchange program will not be used. To note: MSK may join additional HIEs or RHIOs in the future. Any available HIE or RHIO data for participating patients will be collected. PROs are obtained through MSKCC's symptom monitoring software, the same software used to implement symptom self-reporting. Covariates such as age, sex, and race are routinely captured in the MSKCC EMR. Comorbidities are captured by an MSKCC platform used to take the baseline medical history in all surgical patients potentially eligible for ambulatory cancer surgery. Caregivers' responses to the Caregiver Reaction Assessment questionnaires will be

collected via REDCap, a secure web application for building and managing online surveys and databases. In the event the REDCap survey is unavailable, a hardcopy form will be provided to caregivers to complete.

### **Sensitivity analyses to determine the impact of key assumptions and missing data**

The primary threat to validity is a larger than expected number of emergency department visits to outside institutions and reporting that varies systematically between groups (e.g., if patients in the Enhanced Feedback group are less likely to report a visit to a non-MSKCC emergency department). We will conduct sensitivity analyses by first examining whether the proportion of visits to MSKCC vs. non-MSKCC sites varies between groups. We will then determine the number and distribution of unreported emergency department visits that would need to have occurred to change our conclusions (e.g., if we reject the null hypothesis in favor of the experimental arm, we will determine the number of excess unreported visits in the experimental arm that would result in a  $P$  value  $\geq 0.05$ ).

### **Approach to missing data for questionnaire items**

Baseline characteristics between those with and those without missing data will also be compared to assess for bias. The rate of missing data is expected to be low. The main threat to data completion involves the caregiver and patient questionnaires obtained at 2 weeks and 2 months, respectively. In addition to automated electronic reminders, a research assistant will follow up with patients who have missing data. Patients from whom no data are obtained will be classified as “unable to contact,” “too busy/uninterested,” or “intervention related” (e.g., a patient who declines to complete the questionnaires because of an experience earlier in the trial). Patterns of missing data will be compared by treatment arm. In the unlikely event that the rate of missing data is more than 5%, we will impute missing data using multiple imputation by chained equations, with results combined using Rubin’s rules. The principle assumption of such a method is that the data are “missing at random” or “missing completely at random.” It seems at least possible that any missingness will be nonignorable on the grounds that a patient with a poor level of patient activation will be less likely to complete surveys. We will therefore repeat multiple imputation, except instead of missing activation measures being sampled from a distribution centered on the mean they will be sampled from the 25th and, alternatively, 10th percentiles. A similar approach will be taken for the caregiver measure, for comparable reasons.

### **Heterogeneity of treatment effect**

It is possible that the effects of Enhanced Feedback vary predictably between patients. Although it is common to assess computer literacy as an effect modifier in trials of patient-facing software, we believe that this is inappropriate for the current proposal. This is because both groups will interface with the software, and the difference between the two groups is not highly software dependent. It does, however, seem plausible that patient willingness to make proactive decisions about their postoperative care in the light of data about expected symptoms would be mediated by age, educational status, and the type of procedure they undergo. We will therefore repeat all analyses including

interaction terms between allocation and age, education, and procedure. Educational status is obtained routinely at baseline for all MSKCC surgery patients and will be coded as a binary variable: education after high school/high school only. The models will be of the following form (with a linear case being shown for the sake of simplicity):

$$y = \beta_1 \text{ Allocation} + \beta_2 \text{ Age} + \beta_3 \text{ Allocation} \times \text{Age} + \beta(\text{Randomization stratum}) + c$$

Allocation is coded 1 for Enhanced Feedback and 0 otherwise; randomization stratum is a categorical variable. A similar model will be used for educational status and procedure type. We have no particular reason to believe that response to Enhanced Feedback would vary by race and ethnicity, but as a check to ensure that our approach does not inadvertently discriminate, we will conduct exploratory analyses of race and ethnicity using the structure of the model described above.

### **Reporting plan with assessments of internal and external validity**

This is a randomized trial with good allocation concealment, and therefore selection bias can be discounted. Patients, however, will not be blinded. This is not an important issue for the primary endpoint, which is emergency department visits, as this is objectively measured and not susceptible to reporting bias. The question of performance bias in terms of differential patient behavior is complicated by the fact that the *aim* of the trial is to change behavior. Performance bias by clinicians is, however, a concern. For instance, it is plausible that a nurse speaking to a study patient by phone in the days after discharge might make differential recommendations about the necessity of an emergency department visit depending on patient assignment. However, this is an unlikely scenario given the context of nursing care at MSKCC. Nurses call large numbers of patients, both those eligible for the trial (ambulatory care surgery) and those ineligible (e.g., complex operations requiring an in-patient stay), and they are unlikely to know which patients are and are not on trial. Patients might potentially reveal allocation to nurses during the phone call (e.g., “I saw on the website that...”). But, again, as a large number of nurses will be dealing with a large volume of patient calls, it is unlikely that allocation will bias the advice given to a significant extent.

Regarding external validity, the system is currently in use by MSKCC patients, but it is possible that these patients (a referral population in a major urban center) may have higher computer literacy, health literacy, or numeracy than the general population. We recognize that usability barriers that might seem trivial to a highly technology-focused audience can sometimes seem insurmountable for patients facing stress due to illness or treatment or for patients who face preexisting hurdles in terms of computer literacy, health literacy, or numeracy. As a result, we have built in a brief user-centered design stage supervised by coinvestigator [name] to review the existing platform in a systematic fashion, elicit constructive feedback from representative users, and perform rapid-cycle modifications to ensure usability and utility for users. We anticipate that this intensive user-centered design project will successfully adapt the existing instrument.

